11.3.2. Vital Signs

Vital signs include heart rate, respiratory rate, blood pressure, and body temperature and should be consistently measured in either the sitting or semi-supine position. Vital signs will be collected at every on-site visit (Table 1). At the Day 1 and Week 4 visits, vital signs will be taken pre-dose and 2 hours (± 20 minutes) post-dose, during the PK assessments. At all other timepoints, vital signs can be taken irrespective of taking study drug. Vital signs that are clinically significant and not explained by the underlying disease or concomitant medications should be recorded as AEs in the eCRF.

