10.2 Definitions of Baseline and Change from Baseline Values

Unless otherwise specified, baseline is defined as the last non-missing measurement prior to the first dose of study drug.

All ECG assessments at a visit are to be performed in triplicate at each scheduled visit. The baseline value for ECG parameters will be derived as the average of all non-missing values, at the last visit prior to the first dose of study drug. Post-baseline assessments at a visit will be averaged for analysis.

In analyses of pharmacodynamics (PD) parameters, baseline is defined as the average of non-missing values from the screening and baseline visits. PD assessments include the following laboratory measurements based on blood samples (HbF-associated biomarkers and total Hb; biomarkers of RBC hemolysis, adhesion, inflammation, and cardiac stress; RBC indices).

Change from baseline at a post-baseline visit is defined as follows:

- For the ECG parameters: Post-Baseline Average Value – Baseline Average Value
- For PD parameters: Post-Baseline Value – Baseline Average Value
- For all other parameters: Post-Baseline Value – Baseline Value

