10.5 Windowing Conventions

All scheduled study visits are defined relative to Study Day 1, the date of first dose. Scheduled visit windows are defined in [Appendix 3](#). A windowing convention will be used to determine the analysis visit value for a given measurement and will be applicable for all by-visit summaries and analyses for efficacy and safety data. Refer to [Table 2](#) below for specific visit windows.

Table 2 Visit Windows for Efficacy and Safety Analyses

| For all Efficacy (Except for QoL) and PD Analyses | |
|---|--|
| Scheduled Study Visit (Protocol Scheduled Day) | Analysis Visit Window (Study Day) |
| Baseline | ≤ 1 |
| Week 4 (Day 28 ± 5) | 2 to 43 |
| Week 8 (Day 56 ± 5) | 44 to 71 |
| Week 12 (Day 84 ± 5) | 72 to 99 |
| Week 16 (Day 112 ± 7) | 100 to 141 |
| Week 24 (Day 168 ± 7) | 142 to 211 |
| Week 36 (Day 252 ± 7) | 212 to 309 |
| Week 52 (Day 364 ± 7) | ≥ 310 |
| For QoL Analysis | |
| Scheduled Study Visit (Protocol Scheduled Day) | Analysis Visit Window (Study Day) |
| Baseline | ≤ 1 |
| Week 4 (Day 28 ± 5) | 2 to 57 |
| Week 12 (Day 84 ± 5) | 58 to 127 |
| Week 24 (Day 168 ± 7) | 128 to 211 |
| Week 36 (Day 252 ± 7) | 212 to 309 |
| Week 52 (Day 364 ± 7) | ≥ 310 |
| For Safety Analysis | |
| Scheduled Study Visit (Protocol Scheduled Day) | Analysis Visit Window (Study Day) |
| Baseline | ≤ 1 |
| Week 1 (Day 7 ± 2) | 2 to 15 |
| Week 4 (Day 28 ± 5) | 16 to 43 |
| Week 8 (Day 56 ± 5) | 44 to 71 |
| Week 12 (Day 84 ± 5) | 72 to 99 |
| Week 16 (Day 112 ± 7) | 100 to 127 |
| Week 20 (Day 140 ± 7) | 128 to 155 |
| Week 24 (Day 168 ± 7) | 156 to 190 |
| Week 30 (Day 210 ± 7) | 191 to 232 |
| Week 36 (Day 252 ± 7) | 233 to 274 |
| Week 44 (Day 308 ± 7) | 275 to 337 |

| For Safety Analysis | |
|---|--|
| Scheduled Study Visit (Protocol Scheduled Day) | Analysis Visit Window (Study Day) |
| Week 52 (Day 364 ± 7) | 338 to 379 |
| Week 56 (Day 392 ± 7) | ≥ 380 |

Windowing will be applied prior to any missing data calculations. The last non-missing measurement taken prior to the date of first dose (including unscheduled assessments) will be labeled as “Baseline”. Unscheduled or Screening visits that occurred before the baseline visit will not be assigned an analysis visit. The early discontinuation visit will be eligible for allocation to an analysis visit.

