If one or more results for a variable are assigned to the same analysis visit, the result with the date closest to the scheduled day per protocol will be used in the analysis. If 2 measurements in the same analysis visit window are equidistant from the scheduled study day, the earliest measurement will be used in the analysis. If multiple assessments are available on the same day (for the same time point), then the average of the assessment will be used in the analysis. If both central and local assessments of the same lab test are available on the same day, the central result will take precedence over the local result.

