13.5.8.3 Vital Signs

Descriptive statistics (N, mean, SD, median, Q1, Q3, minimum, and maximum) will be used to summarize vital sign parameters (body temperature, systolic blood pressure, diastolic blood pressure, heart rate, and respiratory rate) at baseline, each post-baseline visit, and change from baseline to each post-baseline visit, by treatment group. Study baseline as defined in [Section 10.2](#) will be used.

Potentially clinically significant (PCS) post-baseline vital signs can be identified using the criteria shown in [Table 10](#) below. The number and percentage of subjects with any post-baseline treatment-emergent potentially clinically significant vital sign value will be tabulated by treatment group for each criterion. Any subject with a post-baseline result meeting the criteria, including those collected at unscheduled visits, will be counted.

Table 10 PCS Criteria for Vital Signs

| Parameter | Criteria |
|------------|---|
| Heart Rate | 
 • ≤ 50 bpm and decrease ≥ 15 bpm • ≥ 100 bpm and increase ≥ 15 bpm • ≥ 120 bpm and increase ≥ 15 bpm |
| SBP | 
 • ≤ 90 and decrease ≥ 20 mm Hg • < 140 mmHg and Increase ≥ 20 mmHg • ≥ 140 mmHg and Increase ≥ 20 mmHg • ≥ 160 mmHg and increase ≥ 20 mmHg |

| | |
|-----|--|
| DBP | 
 • < 100 mmHg and Increase \geq 20 mmHg • \geq 100 mmHg and Increase \geq 20 mmHg • \leq 50 mmHg and decrease \geq 15 mmHg • \geq 100 mmHg and increase \geq 15 mmHg |
|-----|--|

A plot will be presented to show the pattern of the SBP and DBP values over time by treatment group. Mean and SE will be presented in the plot. Additionally, spaghetti plots for SBP and DBP values over time will be provided for individual subjects with 1) maximum post-baseline SBP increased \geq 20 mmHg and SBP \geq 150 mmHg and 2) maximum post-baseline DBP increased \geq 20 mmHg and DBP \geq 100 mmHg. A shift plot displaying shifts from Baseline heart rate \leq 100 to maximum heart rate $>$ 100 post-Baseline will be provided for the safety analysis set. All vital signs will be presented in a data listing. All vital sign tables and listings will be reported on the Safety Analysis Set.

13.5.8.4 12-lead ECGs

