The average of triplicates from 12-lead ECGs will be used to evaluate the change from baseline in ECG parameters (heart rate, PR interval, RR interval, QRS duration, QT interval, and QTcF interval). Descriptive statistics (N, mean, SD, median, Q1, Q3, minimum, and maximum) of ECG parameters will be presented for baseline, each post-baseline visit, and change from baseline to each post-baseline visit by treatment group. Study baseline defined in [Section 10.2](#) will be used. At Baseline, Week 1 and Week 4, descriptive statistics will also be presented for change from pre-dose to post-dose. All measurements, including those during unscheduled visits, will be provided in data listings.

The number and percentage of subjects whose QTcF values have met each of the criteria below, will be summarized by treatment group for baseline and post-baseline assessment. Unscheduled visit results, or any single result from the triplicates meeting criteria criterion will be included.

Table 11 PCS Criteria for ECG

| Parameter | Criteria |
|--------------------------------------|--|
| QTcF Interval | 
 • $>$ 450 msec for males • $>$ 470 msec for females • $>$ 500 msec for males and females |
| QTcF Interval Increase from Baseline | 
 • \geq 30 msec • \geq 60 msec |

All ECG tables and listings will be reported using the safety analysis set.

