| 8. Multiple assessments for the same visit | Vital Sign, ECG and Laboratory assessments | 
 All ECG assessments are to be performed in triplicate. Valid assessments will be averaged to get the analysis value for that visit. |

| Category | Description | Data Handling Rule |
|---|--|---|
| | | 
 • Other than for ECG assessments, the last non-missing measurement taken prior to the date/time of first study drug (including unscheduled assessments) will be the analysis baseline. • Windowing will be applied for by-visit analyses. Unscheduled or Screening visits that occurred before the Baseline visit will not be assigned an analysis visit. The early discontinuation visit will be eligible for allocation to an analysis visit. • If one or more results for a variable are assigned to the same analysis visit, the result with the date closest to the protocol scheduled day will be used in the analysis. If 2 measurements in the same analysis visit window are equidistant from the protocol scheduled study day, the earliest measurement will be used in the analysis. • If multiple assessments are available on the same day (or for the same time point for ECG assessments), then the average of the assessments will be used in the analysis. • If both central and local assessments of the same lab test are available on the same day, the central result will take precedence over the local result. • All data will be listed in data listings. |
| 9. Special Lab Value Handling | Lab values with a prefix such as: '>', '<', '+' and 'Less than' Etc. | 
 • '>': use the available original value +0.001 in the analyses. • '<': use the available original value -0.001 in the analyses. • '+': use the available original value without the prefix in the analyses. • '≥': use the available original value in the analyses. • '≤': use the available original value in the analyses. |

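### The 2-hour post-dose vital signs have no mean summary that keeps them intact: on Day 1 they fall in no analysis visit, and at Week 4 two SAP rules conflict, so they are diluted or apparently dropped

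*SAP*

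**What the plan says.** Protocol 11.3.2 sets the timing: "At the Day 1 and Week 4 visits, vital signs will be taken pre-dose and 2 hours" after the dose, within 20 minutes either way. At every other visit vital signs may be taken at any time relative to dosing. The schedule of assessments repeats this in both documents.

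The SAP then contains these rules:

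- **Baseline (10.2, 10.5, Appendix 4 item 8).** For vital signs, baseline is the final available reading before study drug is first taken.
- **Safety windows (10.5, Table 2).** Baseline covers Study Day 1 and earlier, Week 1 covers Days 2 to 15, and Week 4 covers Days 16 to 43. Section 13.5.8 applies these windows to the vital-sign by-visit analyses.
- **Same-day rule, Appendix 4 item 8**, which names vital signs, ECG and laboratory data: "If multiple assessments are available on the same day (or for the same time point for ECG assessments), then the average of the assessments" is used.
- **Same-day rule, Section 10.5**, for all by-visit data: "If multiple assessments are available on the same day (for the same time point), then the average of the assessment will be used".
- **Tie rule, Section 10.5 and Appendix 4.** When two readings in a window are equally far from the scheduled day, "the earliest measurement will be used in the analysis".
- **Vital-sign tables (13.5.8.3).** Descriptive statistics are given "at baseline, each post-baseline visit, and change from baseline to each post-baseline visit, by treatment group". There is no split by time point.
- **ECG tables (13.5.8.4).** For Baseline, Week 1 and Week 4, "descriptive statistics will also be presented for change from pre-dose to post-dose". The ECG parameters include heart rate.

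**The concern.** The readings taken 2 hours after dosing on Day 1 and at Week 4 are the only vital signs in the study with a fixed time after the dose. They are therefore the only ones from which the average acute change in blood pressure can be compared across arms. If the by-visit table leaves them out or blends them with pre-dose values, that comparison is never shown, although the data exist.

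Section 12.3 includes change from baseline in vital signs at the interim analysis, so the interim table inherits the same handling. So does the planned plot of mean systolic and diastolic pressure over time, if it is drawn from windowed visit values. Protocol 5.2.2.3 recommends monitoring of vital signs in studies of this drug. The ECG section already has the summary that is missing here, and the SAP gives no reason for the difference.

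**Working it through.** The documents state no figure on this point, so there is nothing to reproduce. The check is to follow each 2-hour reading through the SAP rules.

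**Day 1.** The reading is dated Study Day 1. By date it can fall only in the Baseline window, since Week 1 starts on Day 2. All three statements of baseline require a reading before study drug was taken, so it is not the baseline value either. It has no analysis visit and contributes 0% to the by-visit means. The baseline value itself is not contaminated.

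**Week 4.** Day 28 falls in the Week 4 window. The pre-dose and 2-hour readings share a date, so they are equally distant from the scheduled day. There are two readings of the SAP:

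- *Appendix 4 item 8 governs.* The limit to the same time point is written for ECG only, so same-day vital signs are averaged.
- *Section 10.5 governs.* The readings belong to different time points and are not averaged. The tie rule then appears to select the earlier one, which is pre-dose.

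Section 6.0 settles a conflict between SAP and protocol. It does not rank one SAP section over another.

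**Size at Week 4.** Let *d* be the effect 2 hours after dosing, and *f* the fraction of it still present before the Week 4 dose. The documents give no value for *f*, so it is varied from 0 to 1.

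- Same-day average: (*f·d* + *d*)/2 = *d*(1 + *f*)/2
- Earliest reading kept: *f·d*
- Separate time points: *d*

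With an assumed *d* of 15 mmHg:

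| *f* | Average | Share kept | Earliest kept | Share kept |
|---|---|---|---|---|
| 0 | 7.5 | 50% | 0 | 0% |
| 0.25 | 9.375 | 62.5% | 3.75 | 25% |
| 0.5 | 11.25 | 75% | 7.5 | 50% |
| 1 | 15 | 100% | 15 | 100% |

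The shares do not depend on the choice of 15 mmHg.

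**Outputs that escape the problem.** The table of potentially clinically significant values in 13.5.8.3 counts any post-baseline result, so it is not tied to the windowed value. To see why this matters, assume a baseline heart rate of 85 bpm and Week 4 readings of 85 pre-dose and 102 post-dose. The individual reading meets the criterion of at least 100 bpm with a rise of at least 15 (102 − 85 = 17). The average, (85 + 102)/2 = 93.5, does not.

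**The case against.** The strongest objection is that little is hidden. Vital signs are summarised descriptively, with no test or interval between arms. Section 13.5.8.3 counts every post-baseline value that meets an outlier criterion. It also plots individual profiles for subjects whose systolic pressure rises by at least 20 mmHg to 150 or more, or whose diastolic pressure rises by at least 20 mmHg to 100 or more. All readings are listed. Protocol 5.2.2.3 reports no blood-pressure change in the phase 2a study. The protocol places the 2-hour readings alongside the PK assessments and does not state that they are there to detect an acute effect. All of this stands, and it keeps the point modest. None of it supplies a mean by arm at 2 hours.

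The tie-rule reading can also be disputed. That rule speaks of distance from the scheduled day, and the next sentence deals with same-day values separately. If it does not apply, Section 10.5 simply fails to say which of the two Week 4 readings is used.

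A reader might infer more than the documents support:

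- *That an acute heart-rate effect is lost.* Section 13.5.8.4 includes ECG heart rate and plans its pre-dose to post-dose change at Baseline, Week 1 and Week 4. Protocol 11.3.5 puts the post-dose ECG at 2 hours.
- *That the Week 4 effect is halved.* That needs the Appendix 4 rule and *f* = 0. After four weeks of daily dosing *f* may well exceed 0: Protocol 5.1 predicts levels above the IC90 for about 22 hours at 300 mg and 24 hours at 400 mg. Target coverage is not a blood-pressure effect, but it rules out assuming *f* = 0.
- *That this can be stated as a loss of power.* No test is planned, and the documents give no SD or pre/post correlation for vital signs.
- *That Section 10.2 mixes pre-dose and post-dose ECGs*, because it says "Post-baseline assessments at a visit will be averaged for analysis". That sentence follows the description of triplicate recordings. Section 13.5.8.4 speaks of averaging triplicates, and Appendix 4 limits ECG averaging to one time point.

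**Conclusion.** The point holds as a gap in the safety reporting, chiefly for blood pressure. The Day 1 conclusion needs no assumption: the 2-hour vital signs enter no by-visit mean. The Week 4 conclusion depends on which SAP rule is followed. Under Appendix 4 item 8, 50% to 100% of a 2-hour effect remains in the visit value. Under Section 10.5 with the tie rule, 0% to 100% remains. Both ranges rest only on *f* lying between 0 and 1. Unless the whole effect persists to the next dose, either rule understates it, and the SAP does not say which rule applies.

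Extreme individual values remain visible, acute heart rate is covered through the ECG, and the efficacy analyses are not touched. The correction is worth making because the SAP as written would give a weaker summary of a timed safety measurement than the data allow.

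**What to change.** 1. Reconcile Appendix 4 item 8 with Section 10.5. State that pre-dose and 2-hour post-dose vital signs are separate time points, and that averaging applies only within a time point.
2. State that the pre-dose reading is the Week 4 value for by-visit change from baseline.
3. Add to Section 13.5.8.3 a descriptive summary by arm of the 2-hour value and of the pre-dose to 2-hour change, on Day 1 and at Week 4, matching what Section 13.5.8.4 already plans for ECG.

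The outlier table and individual plots can stay as they are; a short note that they use individual readings would prevent misprogramming. The cost is SAP wording and one table. No new data, visits or procedures are needed.

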Appendix 5 CTCAE Grade Criteria for Selected Hematology and Chemistry parameters

| Investigations | | | | |
|--|--|---|---|---|
| Laboratory Analyte | Grade | | | |
| | 1 | 2 | 3 | 4 |
| aPTT (activated partial thromboplastin time) prolonged | >ULN - 1.5 x ULN | >1.5 – 2.5 x ULN | >2.5 x ULN | - |
| Alanine aminotransferase increased | >ULN – 3.0 x ULN if baseline was normal; 1.5 - 3.0 x baseline if baseline was abnormal | >3.0 – 5.0 x ULN if baseline was normal; >3.0 - 5.0 x baseline if baseline was abnormal | >5.0 – 20.0 x ULN if baseline was normal; >5.0 - 20.0 x baseline if baseline was abnormal | >20.0 x ULN if baseline was normal; >20.0 x baseline if baseline was abnormal |
| Alkaline phosphatase increased | >ULN – 2.5 x ULN if baseline was normal; 2.0 - 2.5 x baseline if baseline was abnormal | >2.5 – 5.0 x ULN if baseline was normal; >2.5 - 5.0 x baseline if baseline was abnormal | >5.0 – 20.0 x ULN if baseline was normal; >5.0 - 20.0 x baseline if baseline was abnormal | >20.0 x ULN if baseline was normal; >20.0 x baseline if baseline was abnormal |
| Aspartate aminotransferase increased | >ULN – 3.0 x ULN if baseline was normal; 1.5 - 3.0 x baseline if baseline was abnormal | >3.0 – 5.0 x ULN if baseline was normal; >3.0 - 5.0 x baseline if baseline was abnormal | >5.0 – 20.0 x ULN if baseline was normal; >5.0 - 20.0 x baseline if baseline was abnormal | >20.0 x ULN if baseline was normal; >20.0 x baseline if baseline was abnormal |
| Blood bilirubin increased | >ULN – 1.5 x ULN if baseline was normal; > 1.0 - 1.5 x baseline if baseline was abnormal | >1.5 – 3.0 x ULN if baseline was normal; >1.5 - 3.0 x baseline if baseline was abnormal | >3.0 – 10.0 x ULN if baseline was normal; >3.0 - 10.0 x baseline if baseline was abnormal | >10.0 x ULN if baseline was normal; >10.0 x baseline if baseline was abnormal |
| Creatinine increased | >ULN -1.5 x ULN | >1.5 – 3.0 x baseline; >1.5 -3.0 x ULN | >3.0 baseline; >3.0 – 6.0 x ULN | >6.0 x ULN |

| Investigations | | | | |
|--|--|---|---|---|
| | Grade | | | |
| Laboratory Analyte | 1 | 2 | 3 | 4 |
| GGT (gamma-glutamyl transferase) increased | >ULN – 2.5 x ULN if baseline was normal; 2.0 - 2.5 x baseline if baseline was abnormal | >2.5 – 5.0 x ULN if baseline was normal; >2.5 - 5.0 x baseline if baseline was abnormal | >5.0 – 20.0 x ULN if baseline was normal; >5.0 - 20.0 x baseline if baseline was abnormal | >20.0 x ULN if baseline was normal; >20.0 x baseline if baseline was abnormal |
| Blood bicarbonate decreased | <LLN and no intervention initiated | | | |
| Blood lactate dehydrogenase increased | >ULN | | | |
| Hemoglobin increased (a) | Increase in >0 – 2 gm/dL above ULN (a) | Increase in >2 – 4 gm/dL above ULN (a) | Increase in >4 gm/dL above ULN (a) | n/a |
| Anemia (hemoglobin decreased) | LLN- 10g/dL; <LLN – 6.2 mmol/L; <LLN – 100 g/L | <10.0 – 8.0 g/dL; <6.2 – 4.9 mmol/L; <100 – 80g/L | <8.0 g/dL; <4.9 mmol/L; <80 g/L; transfusion indicated | Life-threatening consequences; urgent intervention indicated |
| INR increased | >1.2 – 1.5; >1 -1.5 x baseline if on anticoagulation (use of anticoagulation identified using the B01A ATC code) | >1.5 – 2.5; >1.5 – 2.5 x baseline if on anticoagulation (use of anticoagulation identified using the B01A ATC code) | >2.5; >2.5 x baseline if on anticoagulation (use of anticoagulation identified using the B01A ATC code) | - |
| Eosinophilia | >ULN and >Baseline | | Steroids initiated | |
| Neutrophil count decreased | <LLN - 1500/mm3; <LLN - 1.5 x 10e9 /L | <1500 - 1000/mm3; <1.5 - 1.0 x 10e9 /L | <1000 - 500/mm3; <1.0 - 0.5 x 10e9 /L | <500/mm3; <0.5 x 10e9 /L |
| Lymphocyte count decreased | <LLN - 800/mm3; <LLN - 0.8 x 10e9/L | <800 - 500/mm3; <0.8 - 0.5 x 10e9 /L | <500 - 200/mm3; <0.5 - 0.2 x 10e9 /L | <200/mm3; <0.2 x 10e9 /L |
| Lymphocyte count increased | - | >4000/mm3 - 20,000/mm3 | >20,000/mm3 | - |

| Investigations | | | | |
|--|---|---|---|---|
| Laboratory Analyte | Grade | | | |
| | 1 | 2 | 3 | 4 |
| Leukocytosis (White blood cell increased) | | | >100,000/mm ³ | Clinical manifestations of leucostasis (sic); urgent intervention indicated Note that the spelling is often "leukostasis" in the literature. |
| Platelet count decreased | <LLN - 75,000/mm ³ ; <LLN - 75.0 x 10 ⁹ /L | <75,000 - 50,000/mm ³ ; <75.0 - 50.0 x 10 ⁹ /L | <50,000 - 25,000/mm ³ ; <50.0 - 25.0 x 10 ⁹ /L | <25,000/mm ³ ; <25.0 x 10 ⁹ /L |
| White blood cell decreased | <LLN - 3000/mm ³ ; <LLN - 3.0 x 10 ⁹ /L | <3000 – 2000/mm ³ ; <3.0 – 2.0 x 10 ⁹ /L | <2000 – 1000/mm ³ ; <2.0 – 1.0 x 10 ⁹ /L | <1000/mm ³ ; <1.0 x 10 ⁹ /L |

(a) Definition: A finding based on laboratory test results that indicate increased levels of hemoglobin above normal – i.e. above ULN.

| Metabolism and Nutrition Disorders | | | | |
|---------------------------------------|--|--|--|---|
| Adverse Event | Grade | | | |
| | 1 | 2 | 3 | 4 |
| Hypercalcemia (Calcium Increased) | Corrected serum calcium of >ULN - 11.5 mg/dL; >ULN - 2.9 mmol/L; Ionized calcium >ULN - 1.5 mmol/L | Corrected serum calcium of >11.5 - 12.5 mg/dL; >2.9 - 3.1 mmol/L; Ionized calcium >1.5 - 1.6 mmol/L; symptomatic | Corrected serum calcium of >12.5 - 13.5 mg/dL; >3.1 - 3.4 mmol/L; Ionized calcium >1.6 - 1.8 mmol/L; hospitalization indicated | Corrected serum calcium of >13.5 mg/dL; >3.4 mmol/L; Ionized calcium >1.8 mmol/L; life-threatening consequences |
| Hyperkalemia (Potassium Increased) | >ULN - 5.5 mmol/L | >5.5 - 6.0 mmol/L; intervention initiated | >6.0 - 7.0 mmol/L; hospitalization indicated | >7.0 mmol/L; life-threatening consequences |
| Hypermagnesemia (Magnesium Increased) | >ULN - 3.0 mg/dL; >ULN - 1.23 mmol/L | n/a | >3.0 - 8.0 mg/dL; >1.23 - 3.30 mmol/L | >8.0 mg/dL; >3.30 mmol/L; life-threatening consequences |
| Hypernatremia (Sodium Increased) | >ULN - 150 mmol/L | >150 - 155 mmol/L; intervention initiated | >155 - 160 mmol/L; hospitalization indicated | >160 mmol/L; life-threatening consequences |
| Hypoalbuminemia (Albumin Decreased) | <LLN - 3 g/dL; <LLN - 30 g/L | <3 - 2 g/dL; <30 - 20 g/L | <2 g/dL; <20 g/L | Life-threatening consequences; urgent intervention indicated |
| Hypocalcemia (Calcium Decreased) | Corrected serum calcium of <LLN - 8.0 mg/dL; <LLN - 2.0 mmol/L; Ionized calcium <LLN - 1.0 mmol/L | Corrected serum calcium of <8.0 - 7.0 mg/dL; <2.0 - 1.75 mmol/L; Ionized calcium <1.0- 0.9 mmol/L; symptomatic | Corrected serum calcium of <7.0 - 6.0 mg/dL; <1.75 - 1.5 mmol/L; Ionized calcium <0.9- 0.8 mmol/L; hospitalization indicated | Corrected serum calcium of <6.0 mg/dL; <1.5 mmol/L; Ionized calcium <0.8 mmol/L; life-threatening consequences |
| Hypoglycemia (Glucose Decreased) | <LLN - 55 mg/dL; <LLN - 3.0 mmol/L | <55 - 40 mg/dL; <3.0 - 2.2 mmol/L | <40 - 30 mg/dL; <2.2 - 1.7 mmol/L | <30 mg/dL; <1.7 mmol/L; life-threatening consequences; seizures |
| Hypokalemia (Potassium Decreased) | <LLN - 3.0 mmol/L | Symptomatic with <LLN - 3.0 mmol/L; intervention indicated | <3.0 - 2.5 mmol/L; hospitalization indicated | <2.5 mmol/L; life-threatening consequences |
| Hypomagnesemia (Magnesium Decreased) | <LLN - 1.2 mg/dL; <LLN - 0.5 mmol/L | <1.2 - 0.9 mg/dL; <0.5 - 0.4 mmol/L | <0.9 - 0.7 mg/dL; <0.4 - 0.3 mmol/L | <0.7 mg/dL; <0.3 mmol/L; life-threatening consequences |
| Hyponatremia (Sodium Decreased) | <LLN - 130 mmol/L | 125-129 mmol/L and asymptomatic | 125-129 mmol/L symptomatic; 120-124 mmol/L | <120 mmol/L; life-threatening consequences |

| Metabolism and Nutrition Disorders | | | | |
|------------------------------------|-------|---|------------------------|---|
| | Grade | | | |
| Adverse Event | 1 | 2 | 3 | 4 |
| | | | regardless of symptoms | |

| Renal and Urinary Disorders | Grade | | | |
|-----------------------------|--|---|---|--|
| Adverse Event | 1 | 2 | 3 | 4 |
| Chronic kidney disease | eGFR (estimated Glomerular Filtration Rate) or CrCl (creatinine clearance) <LLN - 60 ml/min/1.73 m ² or proteinuria 2+ present; urine protein/creatinine >0.5 | eGFR or CrCl 59 - 30 ml/min/1.73 m ² | eGFR or CrCl 29 - 15 ml/min/1.73 m ² | eGFR or CrCl <15 ml/min/1.73 m ² ; dialysis or renal transplant indicated |

